5.4.3 Snap-Frozen Biopsies

1. Tissue should be frozen as soon as possible. Optimally, freeze within 30 minutes from resection.
2. Label cryovial according to instructions in section 5.3.1.
3. Using clean forceps place the tissue in a cryovial and freeze the tube in either vapor phase liquid nitrogen, on dry ice, or by immediate placement in a -70 to -80°C freezer. Keep frozen until shipment to the EET Biobank.

5.4.4 DMEM Suspended Biopsies

1. Tissue (core or FNA) should placed on ice immediately following collection.
2. Label cryovial according to instructions in section 5.3.1.
3. Wash tissue with ice-cold DMEM containing 1% penicillin/streptomycin and transfer into labeled cryovial.
4. Centrifuge tissue at 2000rpm x 2 minutes.
5. Resuspended in 50 µL DMEM.
6. Freeze the tube in either vapor phase liquid nitrogen, on dry ice, or by immediate placement in a -70 to -80°C freezer. Keep frozen until shipment to the EET Biobank.

5.4.5 Blood Collection

5.4.5.1 Collection of Blood in cfDNA Streck Tube

1. Label two 10 mL cfDNA Streck tube according to the instructions in section 5.3.1.
2. Collect 20 mL of blood into the pre-labeled tube and gently invert to mix. **Note:** blood must be thoroughly mixed to ensure preservation of specimen.
3. **After collection, blood in cfDNA Streck tubes should never be refrigerated**, as this will compromise the specimen. Blood collected in cfDNA Streck tubes is stable at room temperature.

5.4.5.2 Collection of Blood in EDTA Tube for Plasma Processing

1. Label EDTA tube(s) according to the instructions in section 5.3.1.
2. Collect 10 mL of whole blood in EDTA (purple top) tube(s). After collection, keep blood at 4°C and process immediately (within 30-60 minutes of collection).
3. Process plasma by centrifuging for 10 minutes at 1,200 x g at room temperature.
4. **Using a clean transfer pipette**, transfer 1 mL of plasma into each of the labeled cryovials (using the label printed from the ETCTN Specimen Tracking System or following the instructions in section 5.3.1). Avoid picking up the blood cells when aliquoting by keeping the pipet above the cell layers and leaving a small amount of plasma in the tube. Tightly secure the cap of the vials before storage. Document the

time the plasma is processed.

5. Store plasma cryovials upright in a specimen box or rack in an -70°C to -90°C or colder freezer prior to delivering to laboratory. Do not allow specimens to thaw after freezing. Document the time the plasma is frozen.
6. Record the time the sample was processed to plasma and when the plasma is stored at -80°C.

5.4.5.3 Collection of Blood in EDTA Tube for PK Plasma Processing for Mayo Clinic

1. All “prior to drug administration” samples should be collected after at least 8 hours of fasting. Instruct patients to bring dose to the clinic and take dose (with food) after the baseline PK sample has been obtained on the days where PK sampling will occur.
2. Label both 3 mL EDTA (purple top) tubes for Telaglenastat (CB-839) HCl samples.
3. Collect blood in pre-labeled tube and gently invert tube to mix. Place on wet ice (or store at 4°C) until processing.
4. Blood must be processed for plasma isolation within 20 minutes of collection. The time at which the sample was collected from the patient and the time at which the plasma was stored in an aliquot at -80°C must be recorded in the Specimen Tracking System for every sample to ensure adequate handling.
5. Centrifuge blood at 1,000 – 1,300 x g (relative centrifugal force [RCF]) for 10 minutes in a refrigerated centrifuge kept at 4°C.
6. Following centrifugation, remove the plasma (top yellowish or clearish layer) and create aliquots in equal volumes of at least 0.5 mL in labeled 2 mL screw-top cryovials. Refer to Section 5.4.1.2 for labeling instructions.
7. Tube labels must contain the information indicated in Section 5.4.1.2. These data should be recorded in nurse’s notes, on the flow sheet, and on the pharmacology reporting form that is to be sent with the samples.
8. Freeze vials immediately upright in a -70 to -80°C freezer until shipment to the Mayo Clinic Cancer Center Pharmacology Shared Resource. See Section 5.6 for shipping instructions and address.

5.4.5.4 Collection of Blood in EDTA Tube for Oncometabolite Analysis

1. All “prior to drug administration” samples should be collected after at least 8 hours of fasting. Instruct patients to bring dose to the clinic and take dose (with food) after the baseline oncometabolite sample has been obtained on the days where oncometabolite sampling will occur.
2. Label both 3 mL EDTA (purple top) tubes for Telaglenastat (CB-839) HCl samples.
3. Collect blood in pre-labeled tube and gently invert tube to mix. Place on wet ice (or store at 4°C) until processing.
4. The peripheral blood sample must be centrifuged within 30 to 60 minutes of collection at 4°C with a centrifuge speed of 2000 x g for 15 minutes.
5. After centrifugation, remove plasma (top yellowish or clearish layer) and create 0.5 mL aliquots in labeled 2 mL screw-top cryovials.
6. Immediately freeze the aliquots upright in a -70 to -80°C freezer until shipment to the EET Biobank according to the instructions below. The time at which the sample

was collected from the patient and the time at which the plasma was stored in an aliquot at -80°C must be recorded in the Specimen Tracking System for every sample to ensure adequate handling.

5.5 Shipping Specimens from Clinical Site to the EET Biobank

Core biopsies that are fixed in formalin and fresh blood should be shipped as one shipment at ambient temperature, whenever possible. The same box sent with kit contents should be used to ship specimens to the EET Biobank. In winter months, please include extra insulation, such as bubble wrap, inside the shipping container.

For formalin-fixed biopsies, if the corresponding anatomical pathology report is not available at the time of shipment, then the surgical and/or radiology report must be uploaded to the ETCTN specimen tracking system and included in the package, or the specimen will not be processed.

5.5.1 Specimen Shipping Instructions

Tissue in formalin must be shipped on the day of collection. Collect and ship on Monday through Wednesday.

Frozen specimens may be shipped on Monday through Thursday.

Fresh blood may be shipped on Monday through Friday. Please select “Saturday Delivery” when shipping fresh blood on a Friday.

5.5.1.1 Shipping Blood in an Ambient Shipper

1. Before packaging specimens, verify that each specimen is labeled according to the instructions above and that the lids of all primary receptacles containing liquid are tightly sealed.
2. Prepare the SAF-T-TEMP Gel Pak for shipment. *Note: If contents of the Pak are crunchy, place Pak in a warm water bath until gel is smooth. Do not refrigerate, freeze, or microwave.*
3. Place the SAF-T-TEMP Pak in bottom of insulated chest. Note: The insulated chest must be shipped inside the provided cardboard box(es).
4. Place the blood collection tubes in zip-lock bags.
5. Next, place blood into a biohazard envelope with absorbent material. Expel as much air as possible and seal the envelope securely.
6. Place the biohazard envelope into a Tyvek envelope. Expel as much air as possible and seal securely.
7. Place packaged blood collection tube(s) and a copy of the shipping manifest from the Sample Tracking System on top of SAF-T-TEMP Pak.
8. Place the lid on the insulated chest.

9. Close the outer flaps of the shipping box and tape shut.
10. Attach a shipping label to the top of the shipping container.
11. Attach an Exempt Human Specimen sticker to the side of the box.
12. Ship specimens via overnight courier to the address below. FedEx Priority Overnight is strongly recommended to prevent delays in package receipt.

5.5.1.2 Shipping Frozen and Ambient Specimens in a Dual-Chamber Kit

The Dual Chambered Specimen Procurement Kit is constructed to allow the shipment of frozen (on dry ice) and ambient (room temperature) specimens in the same container. **Dry ice may be placed in either compartment of the kit but should not be put in both.** The dual chambered kit is only used for shipments that contain both frozen and ambient specimens. If formalin-fixed tissue is shipped separately (not in the same shipment as frozen specimens), then it must be shipped using institutional shipping supplies.

- **Frozen specimens** may be shipped on Monday through Thursday. Ensure that sufficient dry ice is included to completely encase the specimens to maintain specimen integrity during shipment.
- **Formalin-fixed tissue** may only be shipped on Monday through Wednesday.

1. Before packaging specimens, verify that each specimen is labeled according to the instructions above and that lids of all primary receptacles containing liquid are tightly sealed. If included in the shipment, formalin jar lids should be wrapped in parafilm.
2. Pre-fill one of the kit chambers about 1/3 with dry ice.
3. Place the specimens in zip-lock bags. Use a separate zip-lock bag for each specimen type.
4. Two biohazard envelopes are provided so that ambient and frozen specimens can be packaged separately.
 - Place the zip-lock bags containing room temperature specimens in a biohazard envelope with absorbent material. Expel as much air as possible and seal the envelope securely.
 - Place the zip-lock bags containing frozen specimens into the other biohazard envelope containing absorbent material. Expel as much air as possible and seal securely.
5. Put each secondary envelope into a Tyvek envelope. Expel as much air as possible and seal each envelope securely.
6. Quickly place the Tyvek envelope containing frozen specimens (*e.g.*, frozen tumor, serum, *etc.*) in the kit compartment that is pre-filled with dry ice. Place the Tyvek envelope on top of the dry ice. Cover the specimens with additional dry ice until the compartment is almost completely full.
7. Place the Styrofoam lid on top to secure specimens during shipment. Do not tape the inner chamber shut.
8. Place the Tyvek envelope containing ambient temperature specimens (*e.g.*, formalin-fixed tissue) in the other kit compartment at room temperature.
9. Insert a copy of the required forms into a plastic bag and place in the kit chamber

with the ambient specimens.

10. Place the Styrofoam lid on top of the kit compartment to secure specimens during shipment. Do not tape the inner chamber shut.
11. Close the outer lid of the Specimen Procurement Kit and tape it shut with durable sealing tape. Do not completely seal the container.
12. Complete a FedEx air bill and attach to top of shipping container.
13. Complete a dry ice label.
14. Attach the dry ice label and an Exempt Human Specimen sticker to the side of the shipping container.
15. Ship specimens via overnight courier to the address below. FedEx Priority Overnight is strongly recommended to prevent delays in package receipt.

5.6 Shipping to the Mayo Clinic Cancer Center Pharmacology Shared Resource

5.6.1 Plasma Pharmacokinetics Instructions

Samples should be processed at the local sites as described in Section 5.3.3.2.

1. Place the plasma specimens in zip-lock bags. Use a separate zip-lock bag for each time point and collection.

2. Place the zip-lock bags in a biohazard bag containing absorbent material. Expel as much air as possible and seal the envelope.
3. Layer the bottom of a Styrofoam container with dry ice until it is approximately one-third full. Place the biohazard bag containing frozen specimens on top of the dry ice. Cover the specimens with the dry ice until the compartment is almost completely full.
4. Insert a copy of the specimen manifest from the Specimen Tracking System into a plastic bag and place in the kit chamber.
5. Place the Styrofoam lid on top to secure specimens during shipment. Do not seal the Styrofoam container.
6. Place the Styrofoam container into a card board box. Close the card board lid with durable sealing tape.
7. Complete a FedEx air bill and attach to top of shipping container.
8. Complete a dry ice label.
9. Attach the dry ice UN1845 label and an Exempt Human Specimen sticker or UN3373 sticker to the side of the shipping container.
10. Arrange for courier pickup. Note: FedEx Priority Overnight is strongly recommended for next day delivery to prevent delays in package receipt.

5.7 Biomarker Plan

List of Biomarker Assays in Order of Priority

Priority	Biomarker Name	Biomarker Assay	Biomarker Type and Purpose	M/O	Timing	Specimen	Quantity Needed	Laboratory
1	NF1-mut or KEAP1-mut/NRF2 mut or LKB1 mutant	CLIA-certified	Integral Testing for enrollment into trial	M	Obtained any time at or after diagnosis	Blood or Tissue*	N/A	Local or commercial CLIA certified lab
2	cfDNA NF1/KEAP1/NRF2-mut /STK11/LKB1 mutant	NGS	Exploratory To explore concordance of the eligibility mutations between tissue and ctDNA	O	Pre-treatment, week 4 and week 8 and at progression	Plasma	2 cell-free DNA (cfDNA) Streck tubes (2 × 10 mL)	NCI MoCha
3	Glutamine/Glutamate Aspartate/Aspargine	MS/LC	Integrated PD effect of Telaglenastat (CB-839) HCl on systemic levels of TCA cycle metabolites in peripheral blood.	M	Cycle 1 D1 and D15 pre-dose and 0.5, 1, 2, 4, and 8 hrs post-dose Week 4 (post-Telaglenastat (CB-839) HCl dose)	Plasma	1 EDTA (purple-top) tube (10 mL) of blood	[name] / Mayo Clinic Cancer Center (Mayo) Metabolomics Resource Core
4	PK	LC/MS for CB-839 HCl metabolites	Integrated To understand PK of Telaglenastat (CB-839) HCl	M	Cycle 1 D1 and D15 pre-dose and 0.5, 1, 2, 4, and 8 hrs post-dose	Blood	1 EDTA (purple-top) tube (3 mL) of blood per sample 12 samples	[name] / Mayo Clinic Cancer Center (Mayo) Pharmacology Shared Resource

5	WES/ RNAseq	WES/ RNAseq	Exploratory To confirm retrospectively eligibility mutations. Hypothesis generating	M/O	Mandatory pre-treatment Optional on week 4 and at progression	DNA, and RNA from FFPE Tissue* Germline DNA from blood in pre-treatment Streck-Tube (control for WES control only)	3-6 cores PBMC from one Streck tube	NCI MoCha
---	-------------	-------------	---	-----	--	---	--	-----------

Priority	Biomarker Name	Biomarker Assay	Biomarker Type and Purpose	M/O	Timing	Specimen	Quantity Needed	Laboratory
			for response and resistance to treatment.			pre-treatment Streck-tube, WES only		
6	RPPA	RPPA	Exploratory To evaluate changes from pre-treatment, during treatment and post treatment specimens	M/O	Mandatory pre-treatment Optional on week 4 and at progression	Frozen Tissue*	1 core	MD Anderson RPPA Core Facility
7	PDX	PDX generation	Exploratory To understand response/resistance mechanisms and evaluate combination therapies for future development	O	Pre-treatment, week 4, and at progression	Fresh tissue frozen in DMEM*	1 core or FNA	[name] laboratory

*Tumor tissue will only be collected from patients who are at least 18 years of age. If available, archival tissue will also be collected for pre-treatment FFPE tissue sample.

5.8 Integrated Correlative Studies

5.8.1 Quantification of Serum Glutamine, Glutamate, Aspartate, Asparagine – Integrated Laboratory Correlative Study

5.8.1.1 Specimen(s) Receipt and Processing at the EET Biobank

Upon receipt, frozen plasma vials will be accessioned, barcoded, and banked in a -80°C freezer until distribution for testing.

5.9 Exploratory/Ancillary Correlative Studies

5.9.1 Circulating tumor DNA (cfDNA) – Exploratory/Ancillary Laboratory Correlative Study #1

5.9.1.1 Specimen(s) Receipt and Processing at the EET Biobank

Upon receipt, plasma will be processed from blood in cfDNA Streck tubes. Plasma will be stored in 1-mL aliquots in a -80°C freezer until distribution for testing.

5.9.2.1 Specimen(s) Receipt and Processing at the EET Biobank

Formalin-fixed tissue at Screening and Week 4, and Progression/Relapse time points will be used for this assay. Tissue in formalin will be processed and embedded upon receipt at the EET Biobank, and slides will be cut from the biopsies. For all tumor specimens, the first section will be stained with H&E for pathology quality control review to assess tumor content; unstained slides will be macrodissected, if needed, and scraped for DNA and RNA co-extraction. DNA will be banked in a stock vial and RNA will be divided into 5 aliquots; all nucleic acids will be stored in a - 80°C freezer until distribution for testing.

DNA will be extracted from blood collected in cfDNA Streck tubes at the Screening time point following plasma processing. DNA will be stored in a -80°C freezer until distribution for testing.

5.9.3 RPPA and PDX – Exploratory/Ancillary Laboratory Correlative Study #3

5.9.3.1 Specimen(s) Receipt and Processing at the EET Biobank

The snap frozen tissue core (Core 3) collected at Screening, Week 4, and Progression/Relapse time points will be used for RPPA analysis. Upon receipt, snap-frozen tissue will be accessioned, barcoded, and banked in a liquid nitrogen vapor phase freezer until distribution.

DMEM suspended core/FNA (Core/FNA 4) from Screening, Week 4, and Progression/Relapse time points will be used for the exploratory PDX generation. Upon receipt, DMEM suspended tissue will be accessioned, barcoded, and banked in a liquid nitrogen vapor phase freezer until distribution.

6. TREATMENT PLAN

6.1 Agent Administration

Treatment will be administered on an outpatient basis. Reported adverse events and potential risks are described in Section 10. Appropriate dose modifications are described in Section 7. No investigational or commercial agents or therapies other than those described below may be administered with the intent to treat the patient's malignancy.

This phase 2 basket clinical trial utilizes single agent CB 839 HCl at the recommended phase 2 dose at 800 mg (Table 2 and 3).

Table 2. Treatment Plan for Telaglenastat (CB-839) HCl as a single agent	
Category	Treatment Plan
Telaglenastat (CB-839) HCl agent dose	800 mg
Telaglenastat (CB-839) HCl administration and schedule	Telaglenastat (CB-839) HCl dose by mouth twice daily, approximately 12 hours apart, immediately after a meal on day 1 to day 28, repeated every 28 days
Duration of treatment	Repeated every 28 days until unacceptable toxicity or disease progression. Refer to Section 6.3 for additional stopping criteria.
Duration of the study	Upon completion of follow-up procedures.
Duration of follow-up	Every 3 months (\pm) 14 days after the last administered treatment dose

If patient develop toxicity then the dose can be reduced as per Table 3.

Table 3. Dose Reductions of Telaglenastat (CB-839) HCl	
Dose Level	Telaglenastat (CB-839) - HCl Dose

Starting dose	800 mg BID
First dose reduction	600 mg BID
Second dose reduction	400 mg BID
Third dose reduction	Discontinue Telaglenastat (CB-839) HCl

The patient will be requested to maintain a medication diary of each dose of medication. The medication diary will be returned to clinic staff at each clinic visit.

6.1.1 Telaglenastat (CB-839) HCl

When taken with food, Telaglenastat (CB-839) HCl has demonstrated a slightly higher (~1.3 fold) absorption, and patients have experienced significantly fewer incidences of elevated LFTs compared to the fasted state. Telaglenastat (CB-839) HCl should be taken with breakfast and dinner, roughly 12 hours apart.

6.2 General Concomitant Medication and Supportive Care Guidelines

Because there is a potential for interaction of Telaglenastat (CB-839) HCl with other concomitantly administered drugs, the case report form must capture the concurrent use of all other drugs, over-the-counter medications, or alternative therapies. The Principal Investigator should be alerted if the patient is taking any agent known to affect or with the potential for drug interactions. The study team should check a frequently-updated medical reference for a list of drugs to avoid or minimize use of. Appendix B (Patient Drug Information Handout and Wallet Card) should be provided to patients if available.

Telaglenastat (CB-839) HCl is metabolized by human hepatocytes primarily through amide hydrolysis. Telaglenastat (CB-839) HCl does not appear to induce CYP drug-metabolizing enzymes and only weakly inhibits CYP2C9 (~40-50% inhibition at 5 μ M) in vitro. Although Telaglenastat (CB-839) HCl is not expected to inhibit CYP2C9 at the exposure levels planned, caution is warranted when administering Telaglenastat (CB-839) HCl to patients taking drugs that are highly dependent on CYP2C9 for metabolism and have a narrow therapeutic index. A list of medications that are CYP2C9 substrates is provided in Appendix D.

Preliminary PK data generated in single agent Phase 1 studies indicate that concomitant use of proton pump inhibitors (PPIs) may reduce absorption of Telaglenastat (CB-839) HCl, resulting in decreased systemic exposure. Although patients are not required to discontinue their use of these agents, the strong preference is for patients to discontinue PPIs prior to joining the study. Antagonists of the H2 histamine receptor (e.g., ranitidine, famotidine, etc.) may be substituted for PPIs. For patients unable to discontinue PPI therapy or that require restarting PPI therapy while on study, administration of Telaglenastat (CB-839) HCl with an acidic beverage (e.g., orange juice) or supplement (e.g., citric acid) may be an option. If an acidic beverage/oral supplement is administered along with the Telaglenastat (CB-839) HCl dose, it should be recorded on the appropriate eCRF, including the identity of the beverage/supplement, dosage, and start and stop dates of administration.

6.3 Duration of Therapy

In the absence of treatment delays due to adverse event(s), treatment may continue until one of the following criteria applies:

- 6.3.1 Disease progression
- 6.3.2 Intercurrent illness that prevents further administration of treatment
- 6.3.3 Unacceptable adverse event(s)
- 6.3.4 Patient decides to withdraw from the study
- 6.3.5 General or specific changes in the patient's condition render the patient unacceptable for further treatment in the judgment of the investigator
- 6.3.6 Clinical progression
- 6.3.7 Patient non-compliance
- 6.3.8 Pregnancy
 - All women of childbearing potential should be instructed to contact the investigator immediately if they suspect they might be pregnant (e.g., missed or late menstrual period) at any time during study participation.
 - The investigator must immediately notify CTEP in the event of a confirmed pregnancy in a patient participating in the study.
- 6.3.9 Termination of the study by sponsor
- 6.3.10 The drug manufacturer can no longer provide the study agent

The reason(s) for protocol therapy discontinuation, the reason(s) for study removal, and the corresponding dates must be documented in the Case Report Form (CRF).

6.4 Duration of Follow Up

Patients will be followed every 3 months (\pm 14 days after the last administered treatment dose or until death, whichever occurs first. Patients removed from study for unacceptable adverse event(s) will be followed until resolution or stabilization of the adverse event.

7. DOSING DELAYS/DOSE MODIFICATIONS

Based on available data, adverse events that are most likely to be observed with Telaglenastat (CB-839) HCl treatment include fatigue, gastrointestinal events (nausea, vomiting, anorexia), photophobia and elevated liver function tests. Careful application of the dose modification guidelines and close observation of the subjects should minimize the potential risk of dosing

with Telaglenastat (CB-839) HCl. The study personnel must be able to recognize and diagnose these potential adverse events and initiate prompt intervention. Guidelines for Telaglenastat (CB-839) dosage modification for clinically significant non-hematological and hematological toxicities that cannot be clearly determined to be unrelated to study drug, as well as for their management, are listed below.

Dose Level	Telaglenastat (CB-839) - HCl Dose
Starting dose	800 mg BID
First dose reduction	600 mg BID
Second dose reduction	400 mg BID
Third dose reduction	Discontinue Telaglenastat (CB-839) HCl

Dose Modification Guidelines for Hematologic Toxicity

Toxicity Grade (CTCAE v5)	Telaglenastat (CB-839) HCl
Grade 3/4 Anemia (< 8.0 g/dL Hgb)	Hold and resume at the same dose level upon resolution to \leq Grade 1 or baseline
Grade 3/4 Neutropenia (ANC < 1000/ μ L)	Hold and resume at the same dose level upon resolution to \leq Grade 1 or baseline.
Grade 3/4 Thrombocytopenia (Platelets < 50,000/ μ L)	Hold and resume at the same dose level upon resolution to \leq Grade 1 or baseline.

ANC = absolute neutrophil count, Hgb = hemoglobin.

Dose Modification Guidelines for Nonhematologic Toxicity

Toxicity Grade (CTCAE v5)	Telaglenastat (CB-839) HCl
Nonhematologic laboratory Grade \geq 3 events determined to be clinically significant and attributable to study drug(s), except for abnormal liver tests	If symptoms are not tolerable, hold and resume at the same dose level upon recovery to \leq Grade 1 or baseline. If toxicity recurs, hold and restart at next lower dose.

Grade ≥ 3 abnormal liver function tests	
Dose reductions should be considered in any patient who develops drug-related Grade 2 elevated ALT, AST, or bilirubin lasting longer than 1 week.
 
A patient who develops Grade ≥ 3 elevated ALT, AST, or bilirubin should have study treatment held and restarted at a reduced dose after ALT, AST, and bilirubin levels resolve to at least Grade ≤ 1 or baseline.
 
In patients with recurrence of drug-related Grade ≥ 3 elevated ALT, AST, or bilirubin at the lowest dose level, study treatment should be discontinued.
 
In patients who develop ALT/AST elevations $> 3 \times$ ULN in combination with a bilirubin elevation $> 2 \times$ ULN without reasonable other explanation, drug-induced liver injury should be suspected and

	treatment interrupted. Reinstitution of study treatment after recovery of ALT, AST, and bilirubin to Grade 1 or baseline level must be discussed and approved by the Drug Monitor.
Non-laboratory Grade ≥ 3 AEs determined to be clinically significant and attributable to the study drug	
For Grade 3 AEs: Hold and resume at the same dose level or the next lower dose level of Telaglenastat (CB-839) upon recovery to \leq Grade 1 or baseline.
 
For Grade 4 AEs: Permanently discontinue Telaglenastat (CB-839).

Telaglenastat (CB-839) HCl treatment may be delayed for up to 2 weeks from the last dose. Delays longer than 2 weeks are allowed only in cases where the delay was due to a non-drug related cause.

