2.2.5 Clinical Safety Summary

NCI Protocol #: 10220
Version Date: January 3, 2025

As of January 23, 2018, 161 patients have received Telaglenastat (CB-839) HCl as monotherapy, and 250 patients have received Telaglenastat (CB-839) HCl in combination with other agents in phase 1 and early phase 2 trials (Investigator's Brochure). Among 59 patients who received Telaglenastat (CB-839) HCl monotherapy on the TID (fasted) schedule over a dose range of 100-1000 mg, two dose limiting toxicities

(DLTs) have been observed: one at 250 mg TID (grade 3 elevated creatinine) and one at 400 mg TID (grade 3/4 elevated liver function tests (LFTs)). No DLTs have been reported on the monotherapy BID (fed state) schedule up to a dose of 800 mg. DLTs reported in combination cohorts have been: Grade 4 neutropenia (400 mg BID with 80 mg/m² IV paclitaxel weekly for three weeks in every four week cycle and 400 mg BID with 4 mg once daily (QD) pomalidomide for 21 days out of every 28 day cycle and 40 mg each week (QW) of dexamethasone), grade 3 pruritic rash (400 mg BID with 10 mg everolimus QD), grade 3 alanine aminotransferase (ALT) increase (800 mg BID with 240 mg IV nivolumab once every two weeks), and grade 4 platelet count decrease (600 mg dose with 60 mg cabozantinib QD). Although a maximum tolerated dose (MTD) has not been defined for either monotherapy or combination therapy, 800 mg BID is the highest dose that is confirmed to be safe and well tolerated in single-agent and combination Telaglenastat (CB-839) HCl studies. The 800 mg BID dose also exhibits robust exposure and pharmacodynamics effects, and has been declared recommended Phase 2 Dose (RP2D).

The largest monotherapy study of Telaglenastat (CB-839) HCl (CX-839-001) included 120 patients, 32 receiving between 100 to 800 mg of Telaglenastat (CB-839) HCl TID without food and 88 receiving between 600 to 1000 mg of Telaglenastat (CB-839) HCl with food (Investigator's Brochure). On the BID schedule, 72.7% of patients experienced an AE, the most common of which were fatigue, elevated LFTs, gastrointestinal AEs, and photophobia. These AEs were typically grade 1/2, reversible, and manageable without dose interruption or modification. Grade 3 LFTs were significantly reduced (2.3% of patients) on the BID schedule. One grade 3 AE of anemia was also considered to be related to Telaglenastat (CB-839) HCl.

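### Section 7 orders no hold for a first, symptom-free Grade 3 or 4 non-liver chemistry abnormality, even when it is judged clinically significant and drug-related

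*Combined protocol and SAP*

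**What the plan says.** Section 7 (Dosing Delays/Dose Modifications) gives one table for hematologic and one for nonhematologic toxicity. The first row of the nonhematologic table covers laboratory events of Grade 3 or higher that are judged clinically significant and attributable to study drug, with liver tests excepted. It contains two instructions:

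- First occurrence: "If symptoms are not tolerable, hold and resume at the same dose level upon recovery to" Grade 1 or lower, or baseline.
- Later occurrence: "If toxicity recurs, hold and restart at next lower dose".

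The neighbouring rows are worded differently. Each hematologic row (Grade 3/4 anemia, neutropenia, thrombocytopenia) says "Hold and resume at the same dose level upon resolution to" Grade 1 or baseline. In the liver row, a patient with Grade 3 or higher ALT, AST or bilirubin "should have study treatment held and restarted at a reduced dose after ALT, AST, and bilirubin levels resolve". The non-laboratory row says "For Grade 3 AEs: Hold and resume at the same dose level or the next lower dose level", and requires permanent discontinuation at Grade 4.

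Below the tables, Section 7 caps delays at two weeks from the last dose: "Delays longer than 2 weeks are allowed only in cases where the delay was due to a non-drug related cause".

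**The concern.** The row applies only after the investigator has decided that the abnormality matters clinically and that the drug caused it. Even then, whether dosing is held at first occurrence depends on how the patient feels. Creatinine, potassium, sodium, calcium, phosphorus and glucose are all in the serum chemistry panel (Section 11, footnote 4), and any of them can reach Grade 3 or 4 without symptoms. None has another row in Section 7.

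A site that works strictly from the table could keep dosing through such a value. The opening of Section 7 relies on careful use of these guidelines to limit risk, so a gap in the table matters even where clinical judgment would usually fill it. What is at stake is the safety of individual patients.

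**Working it through.** No formula applies to the main point. The check takes one case through every row: a first, symptom-free, non-liver chemistry value of Grade 3 or 4, judged clinically significant and attributable.

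| Section 7 row | Does it cover the case? | Symptom condition on a first hold? | Separate Grade 4 action? | Hold ordered for this case? |
|---|---|---|---|---|
| Hematologic, Grade 3/4 | No | None | No | No |
| Nonhematologic laboratory, Grade 3 or higher, non-liver | Yes | Symptoms must be intolerable | No | No, condition not met |
| Liver tests, Grade 3 or higher | No | None | No | No |
| Non-laboratory, Grade 3 or higher | No | None | Yes, discontinue | No |

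The table therefore orders no hold. The non-laboratory row is the closest comparison. It has the same filter (clinically significant and attributable) and still orders a hold at Grade 3 without asking about symptoms.

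The recurrence sentence does not close the gap. It acts only when the toxicity comes back, which presupposes that it went away. Read literally, an abnormality that simply persists without symptoms never reaches it.

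Next, the rest of the protocol was searched for an instruction that would order the hold:

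- Section 6.1 permits dose reduction for toxicity but does not require it.
- Sections 6.3.3 and 6.3.5 allow treatment to end for an unacceptable adverse event or on investigator judgment. They set no grade and are not hold rules.
- Section 10.3.3 requires serious adverse events to be reported within 24 hours. That is reporting only.
- Section 13.1 has the Protocol Principal Investigator review patient-level laboratory data. That is review only.
- Section 11 schedules chemistry weekly in Cycles 1 and 2, on Day 1 only from Cycle 3, and possibly every third cycle for patients stable for at least 13 cycles (footnote 14). This governs how soon a value is seen or repeated, not whether dosing is held.

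Evidence on frequency, from Section 2.2.5 unless stated:

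- One dose-limiting grade 3 creatinine elevation, at 250 mg three times daily, among 59 monotherapy patients dosed fasted. Symptom status is not given.
- No dose-limiting toxicity on twice-daily fed monotherapy up to 800 mg.
- Among 88 patients dosed with food at 600 to 1000 mg in the largest monotherapy study, Grade 3 liver tests (2.3%) and one related grade 3 anemia are reported. No related Grade 3 non-liver chemistry event is mentioned. The text does not say the list is complete.
- Increased creatinine and hyperglycaemia appear among possibly related serious events, pooled over monotherapy and combinations, without grade or counts.
- Section 10.1.1.1 lists creatinine increase, hyperglycemia, hyponatremia and hypophosphatemia among events with insufficient evidence of causation.

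These sources give no count of first, symptom-free events at 800 mg twice daily, so no rate for this trial can be derived from them.

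**The case against.** The strongest reply is that the row already applies only to events judged clinically significant and drug-related. An investigator who has reached that judgment will rarely keep dosing because a guideline table is silent, and Sections 6.1 and 6.3 give authority to reduce or stop. Weekly chemistry in the first two cycles also means an abnormal value is soon rechecked. All this stands, and it makes the path to harm narrow. It does not remove the gap, because the row withholds the instruction after the filter has been passed and no other section supplies it.

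A reader might infer more than the documents support:

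- **That the row requires dosing to continue.** It does not. It is silent, and discretion remains.
- **That the rows of Section 7 contradict each other.** They govern different events. The fault is an unsuitable condition in one row.
- **That the lack of a separate Grade 4 action is part of the defect.** The hematologic and liver rows also pool Grade 4 with Grade 3, and the hematologic rows resume at the same dose. Pooling is this table's normal practice for laboratory events. A Grade 4 rule for chemistry is an optional choice.
- **That 1 of 59 can be projected onto the 108 planned patients.** That event arose at another dose and on another schedule, and whether it was symptom-free is not stated. The documents contain no confirmed instance of the gap.

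**Conclusion.** The point holds as a minor safety correction. For a first, symptom-free, non-liver chemistry event of Grade 3 or 4 that is judged clinically significant and attributable, the dose-modification table orders no hold, and the rest of the protocol only permits one. The condition is unlike any other row in Section 7, and no reason is given for it.

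Frequency is probably low and cannot be estimated from the documents. The twice-daily fed experience is reassuring. The single creatinine dose-limiting toxicity shows that a value of this laboratory type has occurred. Eligibility under Section 3.1.13 also admits patients with raised creatinine if GFR is at least 30 mL/min/1.73 m², so some may enter with reduced renal function.

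The conclusion rests on reading the row literally. If the drafters meant intolerable toxicity rather than intolerable symptoms, the correction is still needed, because the text does not say so. Neither the definition of the primary endpoint nor the operating characteristics of the Simon design are in question.

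**What to change.** In the nonhematologic laboratory row, delete the opening clause about intolerable symptoms so that the action begins with the instruction to hold. Leave everything else as it stands: resumption at the same dose level after recovery to Grade 1 or lower or baseline, the step down on recurrence, and the filter for clinical significance and attribution. The two-week limit already applies. The sponsor may add a Grade 4 action, but this correction does not need one.

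The change is to the wording of one table row and needs no new visits, tests or patients. It would bring a few more interruptions. Some patients would also discontinue when a drug-related abnormality has not recovered within two weeks, which matters because Section 3.1.3 enrolls people with no standard therapy. Occasionally this could remove a patient before response is assessed. Under Section 9.4.2 anyone who has taken one dose stays evaluable, so in a first stage of nine patients that stops on zero responses such a loss is not entirely free. The documents give no basis for counting these cases. The existing filter for clinical significance should keep them few.
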